10. STUDY PROCEDURES AND ASSESSMENTS

All study assessments will be performed at the visits and timepoints outlined in the Schedule of Assessments ([Table 1](#)); the following sections outline the details and procedures associated with the assessments.

10.1. Demographics and Other Baseline Characteristics

10.1.1. Informed Consent

The nature of the study and its risks and benefits will be explained to the subject by the Investigator or designated study personnel. The subject must voluntarily provide written informed consent on an ethics-approved informed consent form (ICF), prior to performing any study-related procedures. The subject's medical records must document that the consent process has been completed and that written informed consent has been obtained from the subject prior to the initiation of any study-specific procedures. Documentation that the subject was given adequate time to ask the Investigator (or designee) questions about their participation in the study and that a signed and dated copy of the ICF was provided to the subject should also be included in the medical records or clinical chart.

10.1.2. Demographics

The following demographics will be recorded: age (birthdate), sex, race, and ethnicity.

10.1.3. Medical and Surgical History

The complete medical and surgical history will include histories of acute, chronic, or infectious disease; surgical or oncologic histories; and any reported conditions affecting major body systems. All findings on medical history will be evaluated by the Investigator for clinical significance.

10.1.4. Medication History

All medications (prescription and non-prescription, herbal medications/natural health products, or investigational drugs) taken by the subjects during the 30 days prior to Screening will be recorded in the source documentation as medication history.

10.1.5. Contraceptive Requirements

Female subjects of childbearing potential must be using and willing to continue using medically acceptable contraception during the study. Examples of medically acceptable forms of contraception include true abstinence, hormonal contraceptives (combined oral pill, patch or vaginal ring, intrauterine device or system, progestin implant or injection), bilateral tubal ligation, or double-barrier methods (i.e., male condom in addition to a diaphragm or a contraceptive sponge).

Female subjects of non-childbearing potential are not required to use contraception or undergo pregnancy tests; however, they must be surgically sterile (hysterectomy and/or bilateral oophorectomy/salpingo-oophorectomy, as determined by subject medical history) or congenitally sterile, or must be post-menopausal. Post-menopausal is defined as being amenorrheic for at least 2 years without another cause.

10.2. Eligibility Review and Randomization

Prior to randomization, subjects must meet all inclusion and not meet any exclusion criteria as outlined in Sections [8.1](#) and [8.2](#).

The Investigator or designee must document that the subjects meet each individual criterion via a signed note or eligibility and inclusion/exclusion checklist during Screening and at Day 1 prior to surgery. Signatures on these documents must be dated on or before the date of randomization on the day of surgery.

Randomization will be accomplished manually.

10.3. Subject Pain Assessment Training

Subjects will undergo study participation education on pain assessments and written testing procedures according to the Schedule of Study Procedures.

10.4. Efficacy Assessments

Details regarding primary and secondary endpoints are provided in Section [10.6](#) (Efficacy Variables); and discussed further in Section [13](#) (Statistical Analysis). The following sections provide an overview of the efficacy assessments included in the study.

10.4.1. Numerical Pain Rating Scale (NPRS) for Pain Intensity

The NPRS is an 11-point scale with anchors 0 (no pain) and 10 (worst possible pain) ([Appendix B](#); [Ferreira-Valente MA et al., 2011](#); [Hjermstad MJ, 2011](#)). Subjects will record the intensity of their current pain at the following times over the initial 48-hour period in a diary: at 0.25, 0.5, 0.75, 1, 2, 4, 8, 12, 16, 20, 24, 28, 32, 36, 40, 44, and 48 hours after the administration of study medication and within 15 minutes prior to use of pain medication. Subjects should be at rest for at least 10 minutes prior to completing NPRS assessments. NPRS Assessments between the hours of 00:00 and 06:00 may be skipped if the subject is sleeping; however, consecutive assessments may not be skipped, and the Hour 12, Hour 24, and Hour 48 assessments must be completed even if the subject is asleep. There will be a ± 5 minute window allowed for the collection of each pain intensity assessment in the first 4 hours after the end of surgery, after which will be a ± 15 minute window allowed.

After discharge and through Day 15, subjects will rate their pain intensity using the NPRS once in the morning (08:00 ± 4 hours) and once in the evening (20:00 ± 4 hours), and will capture an additional NPRS within approximately 15 min prior to each dose of pain medication. Subjects will also rate their pain intensity using the NPRS at the Day 8, Day 15 and Day 29/Early Termination (ET) visit.

10.4.2. Patient Global Evaluation (PGE)

At the clinic visits on Day 8, Day 15 and Day 29/ET, each subject will be asked to report their satisfaction with the study treatment for pain using a 4-point scale. Each subject will be asked the following question: How would you rate the study medication that you have received for pain? Poor (0), Fair (1), Good (2), or Excellent (3). [Appendix E](#)

10.4.3. Investigator Global Evaluation (IGE)

At the clinic visits on Day 8, Day 15 and Day 29/ET, the investigator will report their satisfaction with the subject's study treatment for pain using a 4-point scale. A study Investigator will be asked the following question: How would you rate the study medication that the patient received for pain? Poor (0), Fair (1), Good (2), or Excellent (3). [Appendix F](#)

10.4.4. Brief Pain Inventory-short form (BPI-SF)

At the clinic visits on Day 8, Day 15 and Day 29/ET, the Brief Pain Inventory- Short Form be assessed. [Appendix D](#)

10.4.5. Rescue Medications

The details of rescue medication will be recorded beginning from the end of surgery through 14 days after the end of surgery (Day 15 visit) or to Early Termination Visit. Subjects will be instructed on the proper use and timing of rescue medication.

10.5. Safety Assessments

Safety monitoring will be performed throughout the study for all subjects. All AEs, regardless of causality or severity, will be recorded on the AE CRF.

10.5.1. Clinical Laboratory Assessments

All protocol-specified laboratory tests on blood and urine samples will be performed at a selected central laboratory. The lab will generate laboratory reports and forward them to the clinical site in a timely manner. It is the responsibility of the Investigator to review and sign all lab reports expeditiously, in order to document appropriate safety monitoring of study subjects. The Investigator should sign and date each lab report concurrent with her or his review, and should indicate the clinical significance of each abnormal/flagged value by noting "NCS" (not clinically significant) or "CS" (clinically significant), for example. Notations indicating that a value is clinically significant should also include a brief description of the underlying disease or condition that is associated with the value, e.g., "CS/mild anemia." In general and as determined by the investigator, abnormal, clinically significant laboratory values are expected to be associated with an item recorded in medical history or with an AE.

Blood and urine samples will be collected, processed, and shipped according to instructions from the safety laboratory. Additional laboratory samples may be taken at the discretion of the Investigator if the results of any tests fall outside reference ranges or clinical symptoms necessitate testing to ensure safety. Specific hematology, coagulation, biochemistry, and urinalysis assessments are listed in [Table 4](#).

Table 4 Clinical Laboratory Assessments

Hematology	Biochemistry	Urinalysis
Hematocrit	Sodium	Color
Hemoglobin	Potassium	Turbidity
Red blood cell (RBC) count	Calcium	pH
Total and differential (absolute) white blood cell count	Chloride	Specific gravity
Platelet count	Glucose	Ketones
Coagulation		Creatinine
Activated partial thromboplastin time (aPTT)	Blood urea nitrogen (BUN)	Protein
Prothrombin time (PT)	Albumin	Glucose
International normalized ratio (INR)	Total bilirubin	Bilirubin
	Direct bilirubin	Blood Nitrite
	Alanine aminotransferase (ALT)	Urobilinogen
	Aspartate aminotransferase (AST)	Leukocyte esterase
	Lactic dehydrogenase (LDH)	Microscopic examination of sediment, only if urinalysis dipstick results are abnormal
	Gamma-glutamyl transferase (GGT)	
	Alkaline phosphatase	
	Uric acid	

The clinical laboratory tests will be completed at Screening, Prior to surgery, and at 1.5 hours (± 0.5 hour) after the administration of study medication. In addition to the clinical laboratory tests, a serum pregnancy test will be performed at the Screening Visit and a urine pregnancy test will be performed prior to surgery for women of childbearing potential. ALT or AST $> 3 \times$ ULN / Tot. Bili $> 2 \times$ ULN/ Alk Phos. $> 2 \times$ ULN will be considered an adverse event, as well as any other changes deemed clinically significant by the Investigator.

10.5.2. Urine Drug Screen and Alcohol Breath Test

Urine drug screen and alcohol breath tests will be completed at screening and pre-procedure. All subjects will be tested for drugs-of-abuse (i.e. amphetamines, barbiturates, benzodiazepines, cocaine, opiates, phencyclidine, tetrahydrocannabinol, methadone, methamphetamine, tricyclic anti-depressants, oxycodone and propoxyphene).

The drug and alcohol screens will be performed in-house at the Clinical Unit. If any of these tests are positive, the subject will not be allowed further participation in the trial. However, a positive test may be repeated at the discretion of the PI.

10.5.3. X-Ray

An X-ray of the surgical site will be performed during screening and at Day 29/ET.

10.5.4. Vital Signs

Vital signs will consist of temperature, blood pressure (systolic and diastolic blood pressure, mmHg), pulse rate (beats per minute), and respiratory rate (breaths/min) collected while sitting, following a rest period of at least 5 minutes. Vital signs will be assessed at Screening, Prior to Surgery, and then 0.5, 1, 1.5, 2, 4, 6, 8, 10, 12, 16, 20, 24, 28, 32, 36, 40, 44, and 48 hours after the administration of study medication. Vital sign assessments between the hours of 00:00 and 06:00 may be skipped if the subject is sleeping; however, consecutive assessments may not be skipped, and the Hour 12, Hour 24, and Hour 48 assessments must be completed even if the subject is asleep. There will be a ± 5 minute window allowed for the collection of vital signs in the first 4 hours after the end of surgery, after which will be a ± 15 minute window allowed.

Vital signs will also be assessed on the Days 8, 15 and 29 Follow-up (or at the time of discontinuation). Elevated BP will be defined as SBP > 150 / DBP >95; depressed SBP will be defined as <90; Elevated HR will be defined as HR > 100 / min). If one or more of these measurements is met, and in the opinion of the Investigator is considered clinically significant, it will be considered an adverse event.

10.5.5. 12-Lead Electrocardiogram (ECG)

12-Lead ECGs will be performed after the subject has been resting in a recumbent/supine position for at least 5 minutes. The ECG variables will include ventricular heart rate and the PR, QRS, QT, QTcB and QTcF intervals. The ECGs will be signed and dated by a medically-qualified individual to confirm review of the ECG and verify whether any abnormalities are clinically significant. In general, abnormal, clinically significant ECGs are expected to be associated with an item recorded in medical history or with an AE. ECGs will be assessed at Screening, prior to surgery, and at 1.5 hours (± 0.5 hour) after the administration of study medication. Clinically significant changes in ECG (i.e., QTcF should be <450 msec / < 470 msec for Female / Male subjects respectively; increase of QTcF of 30msec or greater, as well as any other changes as deemed by the Investigator) will be considered an adverse event.

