	
4. Have a known allergy or intolerance to the following medications or related substances: capsaicin, chili peppers, propofol, bupivacaine, benzodiazepines, midazolam, oxycodone, fentanyl or ondansetron.5. Have a clinically significant abnormal clinical laboratory test value that places the subject at an undue risk according to the judgment of the investigator.6. Have, as determined by the investigator or the study's medical monitor, a history or clinical manifestations of significant renal, hepatic, cardiovascular, metabolic, neurologic, psychiatric, or other condition that would preclude participation in the study.7. Use concurrent therapy that could interfere with the evaluation of efficacy or safety, such as any drugs which, in the investigator's opinion, may exert significant analgesic properties or act synergistically with CA-008.8. Use of disallowed pain medications within 2 days prior to Day 1 (NSAIDs, COX-2 inhibitors, tramadol, ketamine, clonidine, gabapentin, pregabalin, or cannabinoids).9. Use of central nervous system (CNS) active drugs such as benzodiazepines, tricyclic antidepressants, SNRIs, or SSRIs for pain within seven days prior to Day 1. These drugs are permitted for non-pain indications if the dose has been stable for at least 30 days prior to Day 1 and is planned to remain stable throughout the study. The use of lorazepam and other sleep medications, except those containing analgesic properties, is permitted.10. Have evidence of a clinically significant 12-lead ECG abnormality according to the judgment of the investigator, including QTcF >450 for men and >470 for women.11. Use of dietary supplements or over-the-counter (OTC) medications containing significant amounts of capsaicin within 1 day prior to Day 1, and throughout the hospitalization period.12. Subjects with active cutaneous disease, or other disease, at the anticipated site of surgery.13. History of peripheral vascular disease, sickle cell disease, vascular grafts, or vasospastic disorders.14. Use of parenteral or oral corticosteroid(s) within 14 days prior to Day 1.
--	---

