	
Safety and tolerability will be evaluated by examining the occurrence of AEs, including Treatment-Emergent AEs. AEs leading to discontinuation from the study, AEs related to the study dose, and AE severity will be summarized by treatment group.
 
Actual and change from baseline in clinical laboratory measures, vital signs, and ECGs will also be assessed and summarized by treatment group. These data will be summarized using descriptive statistics including n, mean, SD, SEM (if appropriate), median, minimum and maximum. Abnormal values will be determined and flagged in the listings. Laboratory shift tables displaying the change (number of subjects) relative to the normal range from baseline to each study visit will also be presented by treatment for each test. The Investigator should exercise medical and scientific judgment in deciding whether an abnormal laboratory finding or other abnormal assessment is clinically significant.
 
The study is not designed to detect a significant difference in analgesia between the two treatment groups. All secondary efficacy endpoints (e.g., NPRS scores), will be summarized over time by treatment using descriptive statistics including confidence intervals as appropriate.

Data Monitoring Committee (DMC):	Safety data will be reviewed by a DMC after the final dosing within each cohort to determine appropriate dose escalation in the next planned cohort.

Table 1 Schedule of Assessments

Assessment	Screening	In Patient					Discharge through EOS	Follow-Up			ET ²
		Prior to Surgery	Surgery	Post-Surgery	24 hr	48 hr		8 ±1 day	15 ±2 days	29 ±2 days	
Study Day	-28 to -1	1	1	1	2	3					
Informed Consent	X										
Screening Medical and Surgical History	X	X									
Inclusion/Exclusion Criteria	X	X									
Screens for alcohol/drugs of abuse	X	X									
Enroll/Randomize		X									
Demographics	X										
Subject Pain Assessment Training	X	X									
Surgery			X								
Infiltration			X								
Safety Evaluations											
Pregnancy Test	X (serum)	X ³ (urine)									
Vital Signs	X	X		X ⁴	X ⁴	X ⁴		X	X	X	X
Physical Exam ⁵	X ⁵	X ⁵		X ⁵	X ⁵	X ⁵				X ⁵	X
12-Lead ECG	X			X ⁶							
Surgical Site assessment	X	X			X ⁷	X ⁷		X	X	X	X
Neurosensory Exam	X	X			X ⁸	X ⁸		X	X	X	X
Blood draw for hematology and serum chemistry/coagulation	X	X		X ⁹							
Urine sample for urinalysis	X	X		X ⁹							
X-ray of Surgical Site	X								X		X
Concomitant Medication Assessment	X	X		X	X	X		X	X	X	X
Adverse Event Assessment	X	X	X	X	X	X		X	X	X	X

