8.2. Exclusion Criteria

Subjects will not be eligible to participate in this study if any one of the following exclusion criteria is met:

1. Subjects with a history of hypertension, cardiovascular disease or a history of cerebrovascular events.
2. Subjects with concurrent painful conditions that may require analgesic treatment during the study period, or, in the opinion of the Investigator, may confound post-operative pain assessments.
3. Have been receiving or have received chronic opioid therapy defined as greater than 15 morphine equivalents units per day for greater than 3 out of 7 days per week over a one-month period within 12 months of study treatment initiation.
4. Have a known allergy or intolerance to the following medications or related substances: capsaicin, chili peppers, propofol, bupivacaine, benzodiazepines, midazolam, oxycodone, fentanyl or ondansetron.

5. Have a clinically significant abnormal clinical laboratory test value that places the subject at undue risk according to the judgment of the investigator.
6. Have, as determined by the investigator or the study's medical monitor, a history or clinical manifestations of significant renal, hepatic, cardiovascular, metabolic, neurologic, psychiatric, or other condition that would preclude participation in the study.
7. Use concurrent therapy that could interfere with the evaluation of efficacy or safety, such as any drugs which, in the investigator's opinion, may exert significant analgesic properties or act synergistically with CA-008.
8. Use of disallowed pain medications within 2 days prior to Day 1 (NSAIDs, COX-2 inhibitors, tramadol, ketamine, clonidine, gabapentin, pregabalin, or cannabinoids).
9. Use of central nervous system (CNS) active drugs such as benzodiazepines, tricyclic antidepressants, SNRIs, or SSRIs for pain within seven days prior to Day 1. These drugs are permitted for non-pain indications if the dose has been stable for at least 30 days prior to Day 1 and is planned to remain stable throughout the study. The use of lorazepam and other sleep medications, except those containing analgesic properties, is permitted.
10. Have evidence of a clinically significant 12-lead ECG abnormality according to the judgment of the investigator, including QTcF >450 for men and >470 for women.
11. Use of dietary supplements or over-the-counter (OTC) medications containing significant amounts of capsaicin within 1 day prior to Day 1, and throughout the hospitalization period.

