13.4.8. Vital Signs and ECG

Descriptive summaries (mean, SD, median, minimum, and maximum) of actual values and changes from Baseline will be calculated for vital signs and ECG. Detailed description of the analysis will be included in the Study SAP.

The incidence of abnormal ECG findings will be summarized for each visit.

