8.3 Clinical Laboratory Evaluation

Clinical laboratory test results (blood chemistry/coagulation, hematology and urinalysis) will be listed for individual subjects. Baseline for clinical laboratory parameters will be defined as the last evaluation before dosing with study treatment. For each individual lab test value, the raw value and change from baseline will be summarized by treatment and time point.

Each clinical laboratory test will be defined by the clinical laboratory to be “Low”, “Normal”, or “High”, according to the normal reference range from the clinical laboratory. The number and percentage of subjects who have a shift from within to outside the normal reference range from baseline (and vice versa) to each follow-up visit will be summarized by treatment and time point.

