8.4 Vital Signs

Vital signs results including BP (systolic and diastolic), pulse rate, respiration rate, and body temperature will be listed for individual subjects. Baseline for vital signs measurements will be defined as the last evaluation before dosing with study medication. Summary statistics, including change from baseline, will be determined for each measure and will be summarized by treatment and time point.

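### Protocol 10.5.5 transposes the sex-specific QTcF limits for an ECG adverse event relative to exclusion 10; secondarily, the SAP names no table for the promised ECG change-from-baseline summary.

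*Protocol*

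**What the plan says.** **Eligibility.** Exclusion 10 in Protocol 8.2 treats "QTcF >450 for men and >470 for women" as a clinically significant ECG abnormality. The synopsis repeats it: "including QTcF >450 for men and >470 for women".

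**Adverse event rule.** Protocol 10.5.5 makes clinically significant ECG changes adverse events and spells them out. The absolute part is "QTcF should be <450 msec / < 470 msec for Female / Male subjects respectively". The rest is "increase of QTcF of 30msec or greater, as well as any other changes as deemed by the Investigator". One post-dose ECG is scheduled, at 1.5 hours.

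**Planned ECG summary in the protocol.** The synopsis states: "Actual and change from baseline in clinical laboratory measures, vital signs, and ECGs will also be assessed and summarized by treatment group". Protocol 13.4.8 states: "Descriptive summaries (mean, SD, median, minimum, and maximum) of actual values and changes from Baseline will be calculated for vital signs and ECG". It also plans the incidence of abnormal ECG findings and leaves the detail to the SAP.

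**Planned ECG summary in the SAP.** For laboratory tests, SAP 8.3 says "the raw value and change from baseline will be summarized by treatment and time point". For vital signs, SAP 8.4 says "Summary statistics, including change from baseline, will be determined for each measure". SAP 8.8 on ECGs speaks only of listing abnormalities and counting subjects with abnormal results. The only ECG table in SAP 14.1.1 is Table 14.3.7, on abnormal findings. SAP 3 states as a general convention that continuous assessments, and their changes from baseline, are summarized by treatment and time point.

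**The concern.** ECG abnormalities and adverse events are both primary safety endpoints, and this is a first-in-human study. A numeric threshold that helps decide what becomes an ECG adverse event should be the intended one. Here it is looser than the entry limit for men and stricter than the entry limit for women, and no section gives a reason for that. A man could leave the range that made him eligible without meeting the absolute limit, while a woman could meet it at a value the protocol accepted at screening. The misclassification therefore runs in opposite directions by sex.

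The analysis plan does not clearly supply a check. Section 10.5.5 uses a QTcF rise as a criterion, but no listed SAP table shows QTcF change by dose. With six active subjects per dose, counts of abnormal findings alone could leave a shift below the limits unseen.

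**Working it through.** The plan states no calculated figure on this point. The check is a side-by-side reading with simple counts.

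**Step 1: put the limits on the same footing.** Section 10.5.5 says what QTcF should be, so the limit is met when the value is not below it: 450 or more in females, 470 or more in males. Exclusion 10 is met above 450 in men and above 470 in women.

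| Sex | Exclusion 10 met if | 10.5.5 limit met if, as written | Whole-msec values where they disagree |
|---|---|---|---|
| Men | > 450 | >= 470 | 451 to 469, not flagged |
| Women | > 470 | >= 450 | 450 to 470, flagged |

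Counts: 469 - 451 + 1 = 19 values in men; 470 - 450 + 1 = 21 values in women. The stated cut-offs differ by 470 - 450 = 20 msec in each sex. These figures give the width of the disagreement, not a number of affected subjects.

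**Step 2: see whether the 30 msec criterion closes the gap.** Two invented cases show that it need not.

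- A man goes from 440 to 465. The rise is 465 - 440 = 25, below 30. As written, 465 < 470, so no numeric criterion is met. With the labels corrected, 465 > 450, so the limit is met.
- A woman goes from 448 to 458. The rise is 458 - 448 = 10, below 30. As written, 458 >= 450, so the limit is met. With the labels corrected, 458 <= 470, so it is not.

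**Step 3: who is affected.** Planned enrollment is 5 x 8 = 40 subjects: 5 x 6 = 30 active and 5 x 2 = 10 placebo. Protocol 5.2 says the first four cohorts had already been studied at Amendment 2, which is up to 4 x 8 = 32. A change to the adverse event wording can reach at most 40 - 32 = 8 subjects prospectively. An analysis of recorded QTcF values can reach all 40.

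**Step 4: compare promised and listed ECG outputs.** SAP 14.1.1 has four results-and-change tables: 14.3.2.1.1 (chemistry/coagulation), 14.3.2.2.1 (hematology), 14.3.2.3.1 (urinalysis) and 14.3.4 (vital signs). For ECG there are none; Table 14.3.7 covers abnormal findings only. The table list runs straight on into the figures, so withheld pages do not explain the gap.

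**The case against.** The strongest case on the other side is that the transposition changes little. The limits sit inside a definition of clinically significant change, a medically qualified person reviews and signs every ECG, and the investigator may call any other change an event. A man at 465 msec is therefore not lost if he is judged significant. Because the rule concerns changes, a woman stable at 455 msec is arguably not captured. No SAP analysis uses the 450 and 470 limits, safety is not formally compared, and the documents give no QTcF distribution from which to estimate how many events would move. All of this stands. It bears on the size of the consequence, not on the error itself.

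A second objection is that correcting the wording now gives Cohort 5 a different adverse event limit from Cohorts 1-4, although Protocol 5.2 says Cohort 5 will be assessed as before. That also stands for the adverse event counts. It is why the comparison across doses should rest on recorded QTcF values, with one set of limits for all cohorts.

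Three stronger readings are tempting and not supported:

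- A reader might infer that the report will lack an ECG change summary. SAP 3 covers continuous assessments and their changes generally, and 8.8 does not expressly depart from it. SAP 3 does give specific sections precedence, but a missing table title is weak evidence that an analysis was dropped: SAP 7.4.6 plans an ANOVA of the global evaluations that the titles of Tables 14.2.6 and 14.2.7 do not mention. What can be said is that 8.8 and the table list do not specify the summary.
- A reader might infer that escalation decisions were compromised. Table 2 in Protocol 8.4 grades ECG and cardiac issues by symptoms and intervention, not by QTcF limits, and under 8.5 the DMC may review ECGs directly.
- A reader might take the mention of a pre-surgery ECG in 10.5.5 as a conflict over baseline. Protocol 10 makes Table 1 govern timing, Table 1 has no such ECG, and baseline is the last pre-dose assessment in any case.

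**Conclusion.** The transposition is real. The word fixing the order in 10.5.5 leaves no ambiguity, and exclusion 10 reads the other way in two places. A stated adverse event threshold on a primary safety endpoint is wrong by 20 msec in each sex: too lenient for men at 451-469 msec and too strict for women at 450-470 msec. This assumes that exclusion 10 carries the intended assignment, which its repetition and the absence of any rationale for reversing it support.

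The practical effect is modest, and its frequency cannot be estimated from the documents. Most of the value lies in applying the corrected limits to values already recorded. The gap in SAP 8.8 and the table list is secondary: a promised summary is left to a general convention and should be made explicit. The point should be fixed but does not threaten the trial.

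**What to change.** 1. Correct Protocol 10.5.5 so that QTcF above 450 msec in males or above 470 msec in females meets the limit, matching exclusion 10. Leave the 30 msec rise criterion and investigator judgement as they are.
2. In the analysis, apply the corrected limits and the criterion of a rise of 30 msec or more to recorded QTcF values from all five cohorts, whatever adverse events were recorded. Cohorts 1-4 and Cohort 5 are then treated alike.
3. Add to SAP 8.8 and the table list one ECG results-and-change table by dose and pooled placebo, parallel to Table 14.3.4. It should give n, mean, SD, median, minimum and maximum of the value and change for each interval, plus the counts from step 2.

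The cost is a wording amendment, which under Protocol 14.6 generally needs IRB approval before it is implemented, and one extra descriptive table specified before database lock. The intervals are already collected, so no assessment is added and the schedule does not change. Adverse event counts from Cohorts 1-4 stay as recorded under the old wording; the report should say so and point to the new table for the comparison across doses.
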